6.3 Previous and Concomitant Medications and Interventions

Concomitant medications and interventions to be summarized for ITT and Safety. Baseline and post-baseline determination will be made programatically in reference to randomization date and assessment date(s).

- Concomitant medications of interest at baseline will be summarized by treatment.
- Post baseline concomitant medications of interest will be summarized by treatment.
- Post baseline concomitant intervention will be summarized by treatment.

6.4 Vitals and Physical Assessments

- Descriptive statistics and change from baseline by treatment at each scheduled visit will be provided through 1 year along with the worst observed value and the best observed value targeted physical exam results and vital signs (pre-dose, post-dose and

30 min post-dose) and: systolic blood pressure (SBP), diastolic blood pressure (DBP), heart rate, and BMI.

- Shift tables for Heart rate, SBP and DBP will be provided for the dosing days through 1 year. Baseline for these shift tables will be the pre-dosing value at the respective visit.

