5.3 IV Medication Precautions

When administering FCM or Placebo, the following precautions will be taken:

- The participant will be evaluated clinically prior to drug administration to assess the development of clinically significant conditions.
- The vials will be visually inspected for particulate matter and discoloration before use. If noted, the vial will not be used, and the Investigator or his designee will notify the sponsor or sponsor's designee for replacement of the study drug, and for direction on the return of the unused vial.
- Heart rate and blood pressure will be assessed pre-, immediately post, and 30 minutes post administration. Participants will be discharged from the site by the Investigator or his or her designee only if there are no significant signs or symptoms 30 minutes after the administration is completed.
- The participant will be monitored for at least 30 minutes for serious acute reactions as hypersensitivity or bioactive (labile) iron reactions to non-dextran IV iron products have rarely been reported. The reactions include: hypotension, loss of consciousness, bronchospasm with dyspnea, shortness of breath, and seizures.
 - In the event a serious acute reaction is seen, the site must have the capability to provide appropriate resuscitation measures. These may include IV NS, IV epinephrine, steroids, and/or antihistamines.

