6.4.3 Additional Study Drug Dosing (Every 6 Months)

All participants will be dosed every 6 months. At each 6-month interval, a course of 2 doses of study drug will be administered as described above for Day 0 and Day 7 (Section 6.3). For group A, FCM will be administered if Hgb < 13.5 g/dL (females) or <15.0 g/dL (males) and serum ferritin <100 ng/mL or 100 to 300 ng/mL with TSAT <20%; observe carefully that placebo (normal saline) will be administered to participants in the FCM group who do not meet the above criteria. All group B participants will receive placebo (normal saline).

6.4.3.1 6 Month Dosing Visit #1 (Days 180 ± 7 , 360 ± 7 , 540 ± 7 , 720 ± 7 , 900 ± 7 , 1,080 ± 7 ...EOS)

On the first of the 2 dosing visits, the following will be performed by blinded study staff for all participants:

- Weight
- Urine or serum pregnancy test (women of childbearing potential only)
- Adverse event / serious adverse event assessment, including evaluation of potential endpoint events (see Section 10.2).
- Review concomitant medications
- Administer 6MWT per standardized procedure (at the 6 and 12 month visits).

Note: To avoid unblinding on the dose administration worksheet, if a participant is under 50 kg, the volume of FCM or placebo administered should be calculated based on the participant's weight, e.g. a 45 kg participant will receive a 13.5 mL dose of FCM or placebo.

For Group A participants the following will be performed:

- Verify if participant will receive FCM or placebo, based on the following criteria from recent labs (within 20 days). Participants will receive FCM if the Hgb <13.5 g/dL (females) or <15.0 g/dL (males) and serum ferritin <100 ng/mL or 100 to 300 ng/mL with TSAT <20%. If the participant does not meet these criteria, placebo (normal saline) will be administered. (unblinded staff)
- As appropriate based on criteria above, verify amount of single FCM dose (15 mg/kg up to a maximum dose of 750 mg) or placebo (15 mL). (unblinded staff)
- Pre-administration, obtain heart rate, blood pressure, and body temperature. (blinded staff)
- Administer FCM or placebo as a slow IV injection at the rate of approximately 2 mL /minute. Appropriate measures must be taken to ensure the participant and all blinded

staff members remain blinded to the treatment being administered (unblinded staff)

- Document start and stop time of IV administration, and the total dose and volume administered (unblinded staff)

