2.2 Safety Population

The Safety population will consist of all ITT participants who received at least 1 dose of study medication identified by the presence of injection start date. When summarizing data using this population, participants are analyzed in the As Treated group. If a participant receives any FCM study drug, then the participant will be counted as treated in the FCM arm, regardless of the amount of medication received; otherwise the participant will be counted as treated in the placebo arm.

The Safety population will be used for assessing Safety.

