6 SAFETY ANALYSIS

There are no *a priori* hypotheses to be tested for safety. Safety will be assessed within the Safety population unless specified otherwise. Nominal visit-based Box and Whisker plots will be produced for continuous safety variables by randomized treatment where applicable. Shift tables for vital signs will be created for dosing days. Supplementary analyses will only be performed where these summaries suggest that there may be clinically significant differences.

For continuous safety parameters, at least one post-randomization measurement is required for inclusion in the analysis. To assess change from baseline, a baseline measurement is also required.

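### Dosing-day heart-rate and blood-pressure tables at the repeat courses are not split by the product injected, so saline given in the FCM arm dilutes any acute FCM effect

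*Combined protocol and SAP*

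**What the plan says.** Protocol version 3, section 5.3, sets the timing of the readings: "Heart rate and blood pressure will be assessed pre-, immediately post, and 30 minutes post administration". It does so among the precautions for acute reactions, where hypotension heads the list.

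SAP v1.3 section 6.4 turns these readings into two outputs. The first is a set of summaries: "Descriptive statistics and change from baseline by treatment at each scheduled visit will be provided through 1 year". The second is the set of dosing-day shift tables: "Shift tables for Heart rate, SBP and DBP will be provided for the dosing days through 1 year". For these, "Baseline for these shift tables will be the pre-dosing value at the respective visit". The shift-table sentence names no column variable.

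The columns therefore follow from the general rules. SAP section 6 says: "Safety will be assessed within the Safety population unless specified otherwise". Section 2.2 defines the groups in that population: "If a participant receives any FCM study drug, then the participant will be counted as treated in the FCM arm". The amount received does not matter, so the label is fixed per participant.

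The product given is not fixed. Under protocol section 6.4.3, at each six-monthly course "placebo (normal saline) will be administered to participants in the FCM group who do not meet the above criteria". Section 6.4.3.2 keeps the second injection of a course on the same product as the first.

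**The concern.** A table whose baseline is the same visit's pre-dose value asks what that injection did within about half an hour. Its columns should then distinguish what was injected. At a repeat course they do not, because a participant given saline that day still counts under FCM if FCM was received earlier.

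The error runs one way: it moves the FCM column toward placebo, so repeat FCM injections look more benign than they are if there is an acute effect.

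The vital-sign data carry more weight here than usual because adverse-event collection is narrow. Protocol 7.2 and SAP 6.1 limit it to serious events and events that lead to stopping study drug. A non-serious fall in blood pressure after a repeat injection would normally be visible only in these readings.

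**Working it through.** The plan gives no figure to reproduce on this point. The check has two parts.

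**1. Which dosing days are affected**

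- Day 0 and Day 7: every FCM-arm participant is due FCM (protocol 5.2), so the column is not mixed by design.
- Day 180 and Day 187: the product depends on the pre-dose laboratory results, and both injections of the course are the same product. Both days are mixed.
- Day 360 and Day 367: the same rule applies. The tables run through one year, so Day 360 is inside and Day 367 is at the edge.
- Day 540 onward: SAP 6.4 plans no such tables.

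Grouping by randomized arm would not help. SAP section 6 does this for another display ("Nominal visit-based Box and Whisker plots will be produced for continuous safety variables by randomized treatment where applicable"), but a switched participant stays in the FCM arm under that rule too.

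**2. Size of the dilution**

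Let f be the share of the FCM column given saline at the visit, and Δ the acute effect of an FCM injection compared with saline. Assume that saline produces the same acute response in a switched FCM participant as in a placebo participant. Then

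excess shown = (1 - f) × Δ + f × 0 = (1 - f) × Δ.

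For f = 20%, 40% or 60%, the table shows 80%, 60% or 40% of Δ. The documents do not state f.

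To show how this affects what a reader could see, assume a given shift occurs in 2% after saline and 4% after FCM, with 1507 per arm (the planned number, so before any attrition). Both rates are assumptions. The rate in the FCM column is (1 - f) × 4% + f × 2%. Power at two-sided 0.05 is used only as a gauge of visibility:

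power = Φ[(difference - 1.96 × SE0) / SE1], with SE0 from the pooled proportion and SE1 from the separate proportions.

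At f = 50% as planned, the rates are 3.0% and 2.0%. SE0 = √(0.025 × 0.975 × 2/1507) = 0.00569 and SE1 = √((0.03 × 0.97 + 0.02 × 0.98)/1507) = 0.00568. Power = Φ[(0.010 - 0.01115)/0.00568] = 42%.

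By product, the FCM-injected group has (1 - f) × 1507 participants, compared with 1507 in the placebo arm, and the rates stay at 4% and 2%.

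| f | FCM-column rate | Excess (points) | Power, as planned | Power, by product |
|---|---|---|---|---|
| 0% | 4.0% | 2.0 | 90% | 90% |
| 10% | 3.8% | 1.8 | 84% | 88% |
| 25% | 3.5% | 1.5 | 71% | 85% |
| 50% | 3.0% | 1.0 | 42% | 77% |
| 75% | 2.5% | 0.5 | 15% | 60% |

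Splitting by product recovers the full effect at every f and gives up only the precision that goes with a smaller FCM group. At small f the two approaches differ little.

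**The case against.** The strongest reply has four parts.

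*The grouping is inferred.* The shift-table sentence names no columns, and SAP section 1 places table specifications in a separate document that is not among those supplied. This stands. A reader might infer that the tables certainly use ever-FCM columns. The documents support only that the SAP's defaults lead there and that 6.4 does not override them.

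*The main acute comparison is intact.* Day 0 and Day 7 are randomized, cover the whole arm and are undiluted. This also stands. A reader might infer that acute FCM effects are hidden throughout the trial, or at every repeat course given. The first reading fails on Day 0 and Day 7. The second fails because the tables stop at one year.

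*Other outputs would catch a problem.* SAP 6.4 also reports worst observed values, section 6 allows supplementary analyses if the summaries suggest a clinically significant difference, and 6.1 tabulates hypersensitivity and infusion-reaction events. The plan is therefore not blind to acute events at repeat dosing. None of these outputs isolates repeat FCM injections, though, and the supplementary analyses would be triggered by the diluted summaries themselves.

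*The by-arm table answers a legitimate question.* The regimen under test is laboratory-guided, and the arm-level contrast describes that regimen. It is also the only randomized comparison at those visits. This stands and is a reason to keep those tables. It does not answer the separate question of what an FCM injection does at re-exposure.

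**Conclusion.** The point holds for the repeat-course dosing days tabulated through one year: Day 180/187 and Day 360, with Day 367 at the edge. Under the SAP's default grouping, the FCM column there mixes FCM and saline injections and shows 1 - f of any acute FCM effect. The dilution is zero only if no FCM participant receives saline at that course.

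The absolute size is unknown, because f and the shift rates are not in the documents. The table of rates and power is illustrative and carries limited weight for outputs that the SAP treats as descriptive, with no prior safety hypotheses. The conclusion also assumes that the separate table specifications do not already split by product injected.

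The efficacy analyses and the Day 0 and Day 7 safety tables are not affected. The protocol's rule for giving saline is not in question. This is a cheap improvement to a safety display.

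**What to change.** In SAP 6.4, keep the by-arm summaries and shift tables at all dosing days. For the repeat-course dosing days through one year, add a descriptive breakdown of pre-to-post changes and shifts in heart rate, SBP and DBP by product injected at that visit: FCM; saline in the FCM arm; saline in the placebo arm. Show the number in each column, which also reports f. Optionally, add a column for placebo-arm participants whose pre-dose laboratory results meet the dosing criteria.

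The cost is a sentence in the SAP and an extra column definition. Unblinded staff already verify the product and document the dose and volume given. SAP 6.5 already plans, by treatment, the frequency of participants outside the dosing criteria before a dosing visit, so the laboratory inputs are at hand; a per-visit flag would have to be stated.

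The downside is that the by-product columns are subsets formed after randomization. FCM participants who still meet the criteria after earlier iron differ from placebo participants who meet them, and matching on current laboratory values does not restore comparability. The breakdown should be labelled descriptive, with Day 0, Day 7 and the by-arm tables as the randomized comparison. If the table specifications already split by product, one sentence in 6.4 saying so is enough.

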6.5 Drug Exposure

The following types of treatment durations will be calculated for FCM and placebo arm.

- Total treatment duration (including days off study drug) = Months between the first and last injection (last injection date – first injection date +1)/30.4375
- Total observation duration = Number of months in the study (date of final study disposition – date of randomization +1)/30.4375.

We will also summarize the total number of infusions received and cumulative dose by treatment for the participants.

Kaplan Meier estimates of time to permanent study drug discontinuation will be summarized by treatment.

Frequency rates of participants, who reach the improved iron indices threshold hemoglobin levels (i.e. participants whose dosing labs are outside the following levels: Hgb <13.5 g/dL (females) or <15.0 g/dL (males) and serum ferritin <100 ng/mL or 100 to 300 ng/mL with TSAT <20% prior to any dosing visit will be presented by treatment. We will also summarize any participants whose treatment was switched due to improved iron indices through the study for FCM arm.

Summaries of duration of treatment, study drug interruption, and drug compliance will be provided by treatment through the overall study period in Safety Population.

6.6 Events of Special Interest related to HF that did not lead to Hospitalization

- All events of interest related to HF that did not lead to hospitalization collected in the study will be summarized by treatment. Specifically, the events are: supraventricular arrhythmia, ventricular arrhythmia, and renal failure, all requiring urgent/emergent intervention.

6.7 Hospitalizations not part of Primary and Secondary Outcomes

- All hospitalizations collected in the study that do not comprise primary or secondary outcomes (non-CV hospitalizations) will be summarized by treatment.

6.8 COVID-19 Related

Any deviations from the protocol related to COVID-19 will be summarized by treatment and a listing will be generated. Listings of all participants recorded as impacted by COVID-19 (related to visit completion, early study or treatment discontinuation, and any reported adverse events of COVID-19 as defined by MedDRA SMQ COVID-19 narrow scope) will also be provided, as appropriate.

6.9 Other Safety Assessments

All adverse events of special interest (ventricular tachycardia, supraventricular tachycardia, and renal failure, all requiring urgent/emergent intervention) will be summarized at participant level by treatment.

If participant or participant's partner becomes pregnant while on the study, the information will be included in the narratives and no separate table will be provided.

7 DATA SAFETY MONITORING BOARD AND INTERIM ANALYSES

7.1 Interim Analyses

The below text regarding interim analyses is as is written in the CSP 1VIT15043, version 3.0, 11 January 2021. The overall alpha levels to be used for primary and top secondary analyses are described in section 1.4.

A Data and Safety Monitoring Board (DSMB) Committee will review safety data, including a tally of the composite outcome events at least every 6 months. The DSMB can recommend stopping the study for safety concern at any point. In addition, one interim analysis is planned to determine if an early stopping for an overwhelming efficacy should be recommended or if an increase in sample size is warranted. The details as identified in Section 8.10 of the protocol are that this analysis will be conducted after 2250 (75%) participants have been randomized. Significance level will be set at 0.0001 for this analysis, resulting in an adjusted significance level for the final analysis of 0.0099 for the primary endpoint and 0.0499 for the first secondary endpoint, preserving the overall significance at 0.01 and 0.05, respectively. Conditional power will be estimated based on data accrued to date and presented to the DSMB.

The DSMB may recommend that the study continues as planned, discontinue the study, or that the trial be continued with recommended changes to the protocol.

The Executive Steering Committee will determine if an increase in sample size is warranted in order that at least 771 participants will experience an event of CV death or hospitalization for heart failure.

8 DATABASE SOURCES

The HEART-FID clinical database will be housed in RAVE Electronic Data Capture (EDC) hosted by Duke Clinical Research Institute (DCRI). In addition, DCRI and KCR will obtain protocol deviation from CTMS, the central laboratory data from Labcorp, and the CEC data from the DCRI CEC group. DCRI will obtain unblinded randomization data collected in the Interactive Web Response System (IXRS) from Almac after the database is locked at the end of the trial.

10 APPENDICES

Additional Appendices may be produced separately and finalised following finalisation of SAP but before database lock.

10.1 Appendix 1: Summary of Amendments to the Protocol relevant to the SAP are here.
Details can be found within the CSP.

Protocol Version 2 and 3:

Affected Sections	Summary of Revisions
Appendix 1	Added a sub-study protocol to evaluate hypophosphatemia.
8.10 Stopping Rules and Interim Analysis	The DSMB may recommend that the study continues as planned, discontinue the study or that the trial be continued with recommended changes to the protocol. The Executive Steering Committee will determine if an increase in sample size is warranted in order that at least 771 participants will experience an event of cardiovascular death or hospitalization for heart failure.
4.5 Discontinuation from Study Drug	Added a definition for a participant permanently discontinued from the study.

- 10.2 **Appendix 2:** Simulations for power estimation for the primary endpoint were conducted at the time of writing the original version of the CSP. The below detailed information was used at the time.

Clinical Rationale: The proposed composite endpoint is intended to capture the clinical effects of the proposed treatment of participants in heart failure with reduced ejection fraction with iron deficiency with or without anemia. From a participant's and clinician's perspective, the essential elements are aimed towards improving the health and well-being of participants with disease as complex as heart failure with reduced ejection fraction. By targeting the experience of participants with heart failure as measured by survival, burden of heart failure hospitalizations, and functional status the proposed composite end-point reflects the key characteristics of a robust composite endpoint ([Anker 2016](#)). The rationale for including the burden of hospitalizations is based on the well-recognized problem that recurrent hospitalizations for worsening heart failure are a common occurrence in participants, and they impose a substantial clinical burden on participants and their families as indicative of worsening of their condition ([Gheorghide 2013](#)). Despite the importance of repeat events, they are often ignored in the majority of clinical trials in favour of 'time to first event' analyses ([Zannad 2013](#)). In addition, heart failure is characterized as a disorder with significant functional impairment in physical activities. One of the most robust assessments of functional impairment that may be feasible on a large scale is the 6MWT ([Forman 2012](#)). This standardized assessment has been used to define functional status and stratify risk for participants in heart failure as well as other conditions such as pulmonary hypertension. The use of this hierarchical, composite endpoint will enable us to provide a more robust and clinically-meaningful classification of participants with heart failure with iron deficiency into those who have improved, remained unchanged, or have deteriorated based on survival, burden of hospitalizations with heart failure, and functional status as measured by the 6MWT distance.

Methods:

Each participant from the treatment arm gets compared with each participant from the control arm based on the 12-month experience to determine treatment response per the following hierarchy:

1. CV death

If both die, the one who survives longer is better off;
If one dies, the one that survives is better off;
If neither dies, examine hospitalizations.

2. Hospitalization for worsening heart failure

The one with fewer hospitalizations is better off;
If number hospitalized equal (both not hospitalized, both with 1 hospitalization etc.), compare 6MWT;

3. Change in 6MWT

The one with higher change in 6MWT is better off;

Statistical Test

The main comparison will be conducted using the Wilcoxon-Mann-Whitney test. The comparison of individuals in the treatment versus control arms is equivalent to ranking all individuals according to their experience. At one end of the ranking are individuals with the best experience - those alive and not hospitalized for worsening heart failure ordered according to their improvement in 6MWT; at the opposite end are those who die ordered according to their survival time. Those alive but hospitalized are in the middle, ordered according to their number

Protocol/Version No.: 1VIT15043/3

Statistical Analysis Plan Version: 1.3 6 March 2023

of hospitalizations for worsening heart failure and then by their change in 6MWT. The non-parametric Wilcoxon-Mann-Whitney test sums the ranks of those in the treatment arm and compares them with the sum of ranks in the control arm.

Table 10.2.1 Assumptions for Sample Size Calculations

Ranked tier at 12-month endpoint	Control	Treatment
Death total	8%	6.8%
Death without hospitalization	4%	3.4%
Death with hospitalization	4%	3.4%
Hospitalizations in survivors		
1	6%	4.8%
2	3%	2.4%
3 or more	1%	0.8%
Change in 6MWT	Mean = 0 SD = 90	Mean = 18 SD = 90
Empirical Power: 0.9500 (N=2930, $\alpha=0.0025$) Clinically-Meaningful Difference: 0.068/0.08 = 0.85		

Conclusion

With 3000 participants (1500 per arm) and 2.5% annual loss to follow up, our simulations estimate $\geq 90\%$ power at various two-sided significance levels between 0.0025 and 0.01.

